Family members represent one potentially powerful resource that could be harnessed to enhance treatment engagement and outcomes. Lack of social support is one of the strongest predictors of the development and maintenance of PTSD (Brewin, Andrews, & Valentine, 2000; Ozer, Best, Lipsey, & Weiss, 2008), and poor family functioning negatively affects treatment outcomes (Evans, Cowlishaw, Forbes, Parslow, & Lewis, 2010; Evans, Cowlishaw, & Hopwood, 2009; Tarrer, Sommerfield, & Pilgrim, 1999). In the case of Veterans, family involvement in mental health services is now a national priority (Department of Veterans Affairs, 2006; New Freedom Commission on Mental Health, 2003), and all mental health providers are encouraged to involve families in Veterans' care (Veterans Health Administration, 2008). However, analysis of data from the VA's national records system showed that only 4.2% of Veterans receiving mental health care in the VA had any type of family session; this included sessions with or without the Veteran present, multi-family groups, or family psychoeducation (Laws & Hoff, 2015). In 2013 family sessions accounted for <1% of all VA mental health visits (Laws & Hoff, 2015), despite social support being associated with 15-20% of the variance in PTSD symptoms (Brewin et al., 2000; Wright, Kelsall, Sim, Clarke, & Creamer, 2013).

(b) Hypotheses or Key Question.

Hypothesis 1: Levels of feasibility and acceptability of the family-inclusive treatment among Veterans, family members, and VA clinicians will be high.

Hypothesis 2a: Patients whose family members receive family-inclusive treatment will show lower levels of PTSD symptoms at post-treatment and greater engagement throughout treatment compared to control patients.

Hypothesis 2b: Family members who receive family-inclusive treatment will show more active support for treatment and less accommodation than control family members.

(c) Specific Objectives. Immediate objectives are to test the feasibility and effectiveness of a family-inclusive intervention for Veterans with PTSD. Longer-term objectives are to examine the mechanisms of family-inclusive treatment and the factors associated with its successful use in VA clinics.

(2) Background and Significance

(a) Background.

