All Veterans enrolled in the study will be beginning a course of either Prolonged Exposure (PE) or Cognitive Processing Therapy (CPT), which will be delivered as usual by PTSD clinical staff. As the BFI is an adjunctive intervention, Veterans' trauma-focused treatment is considered separate from the present study. The Veterans will be seen by regular clinical staff and no artificial limits will be imposed upon their treatment, although treatment engagement will be tracked (see Assessment section, below). Veterans and their family members will be recruited for the present study at the beginning of a course of treatment at the clinic. Phase I will be an open pilot trial of 4 dyads. All family members in Phase I will receive the BFI, which will be delivered as 2 weekly 50-minute sessions of the BFI, consistent with the application with the BFI in previous work (Thompson-Hollands et al., 2015). Phase II will include 20 dyads (N=40) using identical recruitment, inclusion/exclusion criteria, and assessment structure; however, in this second phase family members will be randomly assigned to receive or not receive the BFI, and VABHS clinicians will deliver the BFI sessions (rather than the PI as in Phase I).

Veterans:

Inclusion criteria.

- (1) has a current diagnosis of PTSD

(2) is 18 years of age or older

(3) has an eligible family member (defined as a spouse/significant other, parent, adult child, sibling, etc., 18 years of age or older who currently has substantial daily or weekly contact with the Veteran)

(4) is beginning a course of either CPT or PE at VA Boston.

Exclusion criteria.

(1) has current diagnoses of unstable bipolar disorder, past or present psychosis, or organic mental disorder

(2) has clear and current suicidal risk (assessed via the MINI-Suicide Module (Sheehan et al., 1998), see Assessment section below)

(3) has current moderate or severe substance use disorder

(4) is currently participating in family-based therapy/couples-counseling

Family members:

Inclusion criteria.

(1) is 18 years of age or older

(2) is the family member (defined as a spouse/significant other, parent, adult child, sibling, etc.) of the Veteran

(3) currently has substantial daily or weekly contact with the Veteran

Exclusion criteria.

(1) has a current diagnosis of PTSD

(2) has current diagnoses of unstable bipolar disorder, past or present psychosis, or organic mental disorder

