During the pilot *Phase I* the PI will serve as the BFI clinician. The PI has considerable clinical experience in the treatment of Veterans with PTSD. Additionally, as described above, the PI designed the BFI and has successfully tested its efficacy in a study of patients with OCD and their family members. Beginning in *Phase II* the PI will no longer deliver the intervention; instead, a minimum of 3 clinicians from the VABHS PTSD clinic will be recruited and trained to deliver the BFI.

Comparison condition: Family members in the control or comparison condition of *Phase II* will not receive the BFI or any other study-specific family sessions (aside from the assessments described below). In keeping with the effectiveness aims of the present study, family members in the comparison condition (and the BFI condition) will not be prohibited from receiving any family-inclusive services or sessions that would normally be offered to them in the context of usual VA care.

Independent variables: Receiving or not receiving the BFI (for Veterans/family members); receiving or not receiving training in the BFI (for clinicians).

Dependent variables: Treatment engagement and PTSD symptoms (for patients); accommodation and active treatment support (for family members); qualitative feedback and rates of participation (for Veterans, family members, and clinicians).

Assessment:

Measures and assessment points are shown in Table 1. Qualitative interviews with stakeholders (Veterans, family members, and clinicians) will continue throughout both Phases of the study, as described below. Clinician-rated assessments of Veterans and family members will be completed (in person or via telephone/mail, or a combination of in person and remotely) at baseline and weeks 6, 12, and 16; Veterans and family members will be compensated \$50 for each of these 4 assessment visits that they complete (total of \$200 for the major assessments). Finally, PE and CPT therapists will complete ratings of Veterans' treatment engagement at each session, and will monitor dropout.

Table 1. Assessment Measures and Timepoints

	Time of Administration					
	Baseline	Weeks 0-6	Every PE/CPT session	Week 6	Week 12	Week 16
CAPS-5	X ^v			X ^v	X ^v	X ^v
SCID-5	X ^{v, f}					
Demographics form (Vet/FM)	X ^{v, f}					
Demographics form (Clin)	X ^{tx}					
Relationship information form (Vet)	X ^v					
Relationship information form (FM)	X ^f					
LEC-5	X ^{v, f}					
WTAR	X ^{v, f}					
MOCA	X ^{v, f}					

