The Beck Anxiety Inventory (BAI) (Beck et al., 1988)

The Inventory of Psychosocial Functioning (IPF-80) (Bovin et al., 2018) will be used to index objective role functioning/impairment in the following domains: romantic relationship, family, parenting, work, friendships and socializing, education, and self-care

PTSD Checklist-5 (PCL-5) (Weathers, Litz, Huska, & Keane, 1994)

Revised Conflict Tactics Scale (CTS-2) (Straus, Hamby, Boney-McCoy, & Sugarman, 1996)

Posttraumatic Avoidance Behavior Questionnaire (PABQ) (van Minnen & Hagenaars, 2010)

Posttraumatic Cognitions Inventory (PTCI) (Foa, Ehlers, Clark, Tolin, & Orsillo, 1999)

At each PE or CPT session, the Veteran's therapist will complete (1) a record of session attendance (or dropout, if applicable), along with (2) the Homework Compliance Scale (Leung & Heimberg, 1996) (HCS).

Family member-specific assessments:

Family members will complete/be assessed using the following previously described measures, as outlined in Table 1:

SCID-IV

Demographics form

Relationship information form

AUDIT

LEC-5

WTAR

MOCA

MINI-Suicide module (only administered at follow-up if score was ≥ 1 at baseline, see DSMB section)

RDAS

PCS

MSPSS

DERS

BDI-II

BAI

IPF-80

CTS-2-SF

PCL-5 (family members will rate the PCL-5 based on their perception of the Veteran's current symptoms)

Family members will also complete the following (timing outlined in Table 1):

Significant Others' Responses to Trauma Scale (Fredman et al., 2014) (SORTS)

Caregiving Appraisal Scale (Lawton, Moss, Hoffman, & Perkinson, 2000)

Involvement in Therapy Checklist (ITC). This measure consists of a checklist of involvement in the Veteran's treatment since the last assessment (assisting with therapy homework, driving patient to appointments, attending therapy sessions with the Veteran, etc.).

Treatment Expectancy Questionnaire (TEQ; Borkovec & Nau, 1972). The TEQ will be administered immediately after the first BFI session. Wording was modified slightly to better describe the family program.

The therapeutic alliance following the BFI will be assessed using the 12-item therapist and client versions of the Working Alliance Inventory (WAI; Horvath & Greenberg, 1989; Tracey & Kokotovic, 1989). Wording was modified slightly to better describe the family program.

The Client Satisfaction questionnaire (CSQ) will assess family members' satisfaction with the overall program.

Clinician-specific assessments:

Demographics form

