Participants will be told the exact nature of the study cannot be revealed to them until completion of the follow-up visits to reduce any bias in the results. Any participant withdrawing early from the experiment will be provided with a debriefing at the time of withdrawal.

This application also involves clinician participants currently working in a VA Boston mental health clinic and regularly providing CPT and/or PE ($n \leq 20$). This part of the proposed study involves: (1) Conducting qualitative interviews with providers regarding family-inclusive PTSD treatment; (2) providing training to providers in the delivery of the BFI; (3) collecting recordings of BFI sessions for the purposes of training and measuring fidelity; and (4) notes and recordings from supervision. Clinicians administering the BFI in Phase II will be asked to complete qualitative interviews at posttreatment and turn in audio recordings of sessions. Data in the form of ratings of digital audio recordings of BFI sessions will be collected from the clinicians to monitor their in-session use of the BFI and assess modifications/adaptations to the protocol. These digital audio recordings will either be hand-delivered to the PI (on the recording device) for her to upload onto a secure research drive, or the recordings will be uploaded to a subfolder on the research drive by the clinicians themselves. Each clinician will have access to a dedicated subfolder on the PI's research drive in which to deposit session recordings; these personal subfolders will also include any training materials or other relevant study information from the PI to the clinician. Clinicians will be therapists who are providers in the VA Boston Healthcare System. Thus they will be over 18, as they will need to have completed their training to become therapists.

b. Sources of research materials

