The clinician participants may receive benefit from the training in a new brief family intervention, from access to expert consultation on the intervention, and/or by providing feedback about the potential barriers that require addressing within the mental health clinics. Providers who participate in the treatment portion of the study will receive free training in a new psychotherapy intervention, and this training will also be made available to clinicians who would like the training but do not wish to provide the intervention in the context of the study. Over the longer term, they may also benefit professionally (e.g., future job opportunities at agencies that value family-inclusive approaches to treatment) from the training. Consequently, the potential risks of participation in the study are outweighed by the potential benefit to the participants.

4. Importance of the Knowledge to be Gained

PTSD is a significant public health problem, with national lifetime prevalence rates of 8% (Kessler et al., 1995) and estimated rates in Veterans of the current conflicts in Iraq and Afghanistan of 13-20% (Kok et al., 2012). Family members may serve as a unique resource that can be harnessed to improve outcomes for PTSD treatment; social support is one of the most important predictors of the development and maintenance of

PTSD(Ozer et al., 2008), and family members may provide substantial practical and emotional support for treatment. However, relatives may also inadvertently behave in ways that contribute to the maintenance of the disorder(Erbes et al., 2008). The proposed study will examine a brief family intervention (BFI) delivered in conjunction with individually-delivered trauma-focused treatment.

5. Data Safety and Monitoring Plan (DSMP)

a. Data Monitoring Plan. Data will be collected using standardized forms and will only be identified using the participants' ID number (no names or identifying information will be on the forms). A username and password is required to gain access to the network server, permission is needed to access the data drive, and a separate password is needed to gain access to the database. Data will be stored on a VABHS server (VHABOSCLURES1) and is backed up nightly; no data will be stored on a hard drive.

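### Control families are not to receive the BFI, but training is open to non-study clinicians with no timing rule, separation or record of family-only sessions, so contamination could go unseen

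*Combined protocol and SAP*

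**What the plan says.** Four parts of the document bear on this.

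- **Control condition** (Work Proposed, Comparison condition). Control families "will not receive the BFI or any other study-specific family sessions (aside from the assessments described below"). The next sentence says that families in both arms "will not be prohibited from receiving any family-inclusive services or sessions that would normally be offered to them" in usual VA care.
- **Who is trained.** For Phase II, "a minimum of 3 clinicians from the VABHS PTSD clinic will be recruited and trained to deliver the BFI" (Work Proposed, BFI). Clinician participants, at most 20, are described as "currently working in a VA Boston mental health clinic and regularly providing CPT and/or PE" (Human Studies Section, 1a). The section on potential benefits (Human Studies Section, 3) extends the offer: "this training will also be made available to clinicians who would like the training but do not wish to provide the intervention" as part of the study. It gives no date and no condition on later use.
- **Entry restriction.** A Veteran or family member is excluded if he or she "is currently participating in family-based therapy/couples-counseling". This applies at entry; nothing comparable is stated for follow-up.
- **Measurement.** The Involvement in Therapy Checklist (ITC), completed by family members at weeks 6, 12 and 16, covers involvement in the Veteran's treatment. Its last listed example is "attending therapy sessions with the Veteran, etc". BFI sessions, by contrast, are held with the family member alone (Background, The Brief Family Intervention).

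**The concern.** The randomized contrast is BFI against no BFI. The plan states the control condition but gives no means of securing it once other staff at the same site have been trained. Veterans are recruited from VA Boston outpatient mental health clinics, clinic staff deliver their PE or CPT, and the clinicians eligible for training give those same treatments there. Nothing stops a trained clinician, whether a study clinician or not, from being a control Veteran's therapist.

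The intervention is also easy to carry over. It takes two sessions, can be done by telephone, and uses ideas that the plan itself says CBT clinicians already know. A therapist who has learned it might use parts of it with a control family without regarding that as delivering a study intervention.

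The family-member outcomes in Hypothesis 2b, accommodation and active support, are the BFI's direct targets and would be affected first. PTSD symptoms and engagement in Hypothesis 2a would follow. The plan intends its Cohen's d and confidence interval to serve as a benchmark for later trials, so a shrunken d would be carried forward. Without exposure data no sensitivity analysis could examine it.

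**Working it through.** The plan gives no power figure, target effect or contamination rate, so there is no design figure to reproduce. What follows is an illustration.

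**Inputs from the document**
- Phase II has 20 dyads, half assigned to the BFI: 10 per arm.
- Two-sided alpha is 0.05 (Overview of data analysis).
- The analysis is intended to be intention-to-treat (Hypothesis 2a-2c analytic strategy), so an exposed control stays in the control arm.
- The only between-arm effect size given is d = 1.27, from the OCD trial of 18 dyads (Work Accomplished).
- The only base rate is for VA mental health care generally: "only 4.2% of Veterans receiving mental health care in the VA had any type of family session".

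**Assumptions**
- A share c of control families gets the full BFI effect; c runs from 0 to 30%.
- The true d is 1.27, with 0.8 and 0.5 added to show the range. None of these is a design assumption of this trial.
- There is one comparison at one time point.

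**Formulas**
- Observed effect: d × (1-c).
- Power: noncentral t with 18 degrees of freedom, critical value 2.101, noncentrality d(1-c) × √(10/2) = 2.236 × d(1-c).
- Factor by which a later trial's sample size grows if it is planned on the diluted d: 1/(1-c)².

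**Example.** With d = 1.27 and c = 10%, the observed d is 1.27 × 0.90 = 1.14, the noncentrality is 2.56 and power is 67.6%.

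| c | d seen if true d = 1.27 | Power, d = 1.27 | Power, d = 0.8 | Power, d = 0.5 | 1/(1-c)² |
|---|---|---|---|---|---|
| 0 | 1.27 | 76.6% | 39.5% | 18.5% | 1.00 |
| 4.2% | 1.22 | 73.0% | 36.8% | 17.4% | 1.09 |
| 10% | 1.14 | 67.6% | 33.2% | 15.9% | 1.23 |
| 20% | 1.02 | 57.5% | 27.3% | 13.5% | 1.56 |
| 30% | 0.89 | 46.9% | 22.0% | 11.5% | 2.04 |

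**Exposure at the base rate.** At 4.2%, the expected number of controls with any family session is 10 × 0.042 = 0.42. The chance of at least one is 1 - 0.958^10 = 35%. That rate counts family sessions of every kind and predates BFI training, so actual exposure to BFI content could be lower or higher.

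**Set against sampling error.** With 10 per arm and d = 1.27, the standard error of d is about √(2/10 + 1.27²/40) = 0.49. One exposed control in ten shifts d by 0.13, about a quarter of that. Three in ten shift it by 0.38, about three quarters.

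If exposed families get only a fraction f of the effect, (1-c) becomes (1-cf) and the loss is smaller. Repeated measures would change the power figures but not this shrinkage.

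**The case against.** A reader might infer that the plan permits control families to receive the BFI, because usual-care family services remain open to them. The text does not support that. The control condition excludes the BFI outright, and the allowance covers only what would normally be offered. The plan calls the BFI a new intervention, so giving it to a control family would breach the protocol.

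A reader might also infer that the effect is diluted. That is not established either. The training offer sits in a statement of benefits and gives no timing, so the extra training may come after follow-up. Exposure would need a control Veteran's therapist to take optional training and then use it with the family, and family sessions of any kind are rare in the plan's own figure. Exposure of 10% to 30% is well above 4.2% and is assumed. The power figures borrow an effect from another disorder and use a single t-test, whereas the plan fits a multilevel model to four time points in a study that calls itself preliminary. Sampling error in d is larger than the likely bias. Exit interviews with families and clinicians might also bring off-study sessions to light.

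All of that limits the size of the point. It does not supply the missing safeguard. Stating that controls will not receive the BFI expresses intent; no provision delays the extra training, separates trained clinicians from control dyads, or counts family-only sessions by arm. The ITC's list is open-ended but is framed around the Veteran's own treatment, and the interviews are not described as recording exposure.

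**Conclusion.** The point stands as a gap in safeguards and measurement. The plan excludes the BFI from the control arm, opens BFI training to other clinicians at the same site without a timing rule, and would have no systematic record if BFI content reached control families. Any such exposure that benefited those families would pull the intention-to-treat effect toward zero by the factor (1-c).

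The size is uncertain because c is unknown. At the document's base rate the loss is small, about 4 percentage points of power at d = 1.27. One exposed control in ten costs about 9 points, and three in ten about 30. These figures rest on a borrowed effect size, full effect in exposed controls and a single-endpoint test. Since the study claims no power, the more lasting consequence is for the effect size handed to the next trial, and for the inability to say whether it was diluted. The remedy is cheap enough to be worth adopting.

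**What to change.** Three changes:

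1. In the section on potential benefits, offer BFI training to non-study clinicians only after the last Phase II dyad has completed week 16.
2. Under Comparison condition, state that BFI-trained clinicians do not use BFI content with control families, and that ordinary usual-care family services remain allowed in both arms.
3. At weeks 6, 12 and 16, add an item in both arms recording any family session since the last assessment, with or without the Veteran present, and report exposure by arm.

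If non-study clinicians have already been trained, the second and third changes are still useful.

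The cost is that interested non-study clinicians wait until follow-up ends, and one short item is added at three existing visits. Training of the study's own BFI clinicians is unaffected. Any Aim 1 information expected from training other clinicians would come later.
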